- c. Behavioral assessments will be carried out by trained interviewers/therapists ([name], M.S.W., [name], M.A., [name]., [name], M.A., [name], M.A., [name], M.S.W.) under the supervision of [name].
- d. Computer-assisted Behavioral Therapy. Monitoring and discussion of the computer delivered coping skills treatment program will be carried out by trained interviewers/therapists ([name], M.S.W., [name], M.A., [name]., [name], M.A., [name], M.A., [name], M.S.W.) under the supervision of [name].

General Design:

155 subjects whom meet criteria for cocaine dependence, and all other study inclusion and

NEW YORK STATE PSYCHIATRIC INSTITUTE INSTITUTIONAL REVIEW BOARD

exclusion criteria (described above) will begin a 4-week computer-assisted behavioral intervention. Those participants not responding to the behavioral intervention will begin a 10-week double-blind, placebo-controlled treatment trial. Subjects will be randomized to receive either placebo or MAS-ER. Table 1 shows the overall design

1. Design Overview

We will investigate the effect of augmenting a self-directed version of the Community Reinforcement Approach (CRA; Budney & Higgins, 1998) with Mixed Amphetamine Salts-Extended Release (MAS-ER) to improve treatment response among cocaine dependent patients who do not benefit from the behavioral intervention alone. Patients who do not respond by week four of the CRA+CM intervention will be randomized to a 10-week double blind design to test the combined effects of CRA+CM/MAS-ER against a CRA+CM/PLACEBO control condition. Participants who are randomized to the combination behavioral treatment and medication arm (CRA+CM/MAS-ER) will have their dose titrated to 60 mg MAS-ER daily (over 2 weeks) and maintained on this dose through week 13 of the trial. During week 15, participants will be tapered off the medication (see Table 1. below). Patients responding to the CRA+CM intervention in the first four weeks of treatment will continue with the behavioral intervention and be assessed in parallel to the two (CRA+CM/MAS-ER and CRA+CM/PLACEBO) enhanced treatment arms.

Randomization: Those patients randomized to the placebo group will continue to receive CRA+CM and placebo throughout the treatment. Patients randomized to the CRA+CM/MAS-ER group will begin receiving medication at the start of week 5 and will receive a stable dose of MAS-ER by study week 7.

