- [C13. Exploratory hypotheses: Investigating Mechanisms of Change: We propose a set of exploratory analyses to evaluate the predictive and/or moderating relationship of several key cognitive, verbal, and behavioral mechanisms on treatment response. These variables will be assessed at Baseline, Week 5 (beginning of the medication phase), and Week 14 (end of study). They include: COGNITIVE MECHANISMS. A. Executive Functioning. Self-regulation has been linked to higher order cognitive processes under the rubric of executive functioning, which predicts treatment response (Aharonovich et al., 2006). Within this domain several constructs have been implicated in substance use and treatment response 1. Working memory (Letter-Number Sequencing, Wechsler, 1997), improved working memory is associated with enhanced striatal dopamine release (Backman et al., 2011) and has been implicated as being an important process in treatment outcome (Bickel et al., 2010); The letter number sequencing task will be utilized to assess a participant's working memory. 2. The discounting of delayed rewards (Delayed Discount Program, Robles et al., 2008): Working towards greater delayed rewards in contrast to smaller more immediate rewards is a hallmark characteristic of planned, controlled behavior. However, drug dependent individuals discount future rewards faster than non-dependent individuals and the rate of discounting predicts treatment response (Washio et al., 2011). Area Under the curve (AUC) values will be used to quantify the rate of discounting for each individual. 3. Wisconsin Card Sort, a measure of executive functioning and cognitive

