flexibility, has been related to changes in commitment language during treatment (Aharonovich et al. 2008) and is currently being used in other funded studies (NIDA K23; An experimental model of human language and cognition in drug dependence PI: [name]). 4. The Behavior Rating Inventory of Executive Function (Adult Version (BRIEF-A; Rabin et al., 2006) is a 75-item standardized self-report measure that assesses an individual's perception of their self-regulation in their everyday environment. It yields nine reliable subscale scores reflecting executive functioning (e.g. inhibit, self-monitor) and two broader indices: Metacognition and Behavioral Regulation. The Behavioral Regulation score is the measure of interest, B. Implicit Cognition. We have shown that a stronger attentional bias towards cocaine related stimuli and stronger implicit beliefs about the positive consequences of cocaine use predict worse treatment outcome during behavioral interventions ([name] et al., 2006, 2012). The **Drug Stroop task** has been utilized by our group in other treatment studies ([name] et al., 2006) and will assess the strength of an attentional bias towards cocaine stimuli. The Implicit Relational Assessment Procedure (Barnes-Holmes, 2008) will assess the strength of implicit beliefs about the positive and negative consequences of cocaine use. **BEHAVIORAL** MECHANISM: Relapse Prevention Skills: Coping Strategies Scale (CSS) - Brief Version. (4 mins) (Litt et al., 2005) The utilization of coping skills is central to behavioral interventions for substance use. We will assess the extent to which patients report using the coping skills taught in the TES intervention. The CSS is a 23-item questionnaire (originally adapted from the Processes of Change questionnaire, Prochaska et al., 1988) that assesses coping skills such as problem solving and dealing with urges to use substances of abuse. This scale will be of primary importance to assess the extent to which the treatments differentially impact the development of coping skills. VERBAL MECHANISM: Commitment Language: Language is the primary vehicle of counseling interactions and it promotes self-regulation (Hayes et al., 1986). The strength of in-session commitment language predicts treatment outcome among substance abusers over a one-year period (Amrhein et al., 2003). Patient language will be coded with [name] (a consultant for this proposal) system at baseline and at week 5 (the first week individuals would be randomized to either MAS-ER or PLACEBO) and relate these assessments to treatment outcome. The DARN-C coding is reliable (Amrhein et al., 2003), [name] lab will code the therapy sessions; coders will be blind to patients outcomes and treatment assignments. For this set of analyses Baseline and Week 5 assessments will be used to predict treatment response (multiple comparison corrections will be used to reduce the chance of Type I errors).]

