
C14. Exploratory Analyses. A series of analyses will also be conducted to investigate the effect of each treatment condition on the key cognitive domains assessed and coping skills over time. The analysis of secondary outcomes collected over time will be based on Mixed Effect Models (MEM) for longitudinal data (Diggle et al., 2002). MEM requires no parametric distributional assumptions, provides robust inference with respect to misspecification of the covariance, and allows for the analysis of continuous, categorical and count data which may be missing for some patients either because of a missed week or due to drop-out, thus complete information for all patients is not needed. PROC NL MIXED or GLIMMIX in SAS will be used to carry out these analyses. The analyses will be used to separately test the effect of treatment condition on the magnitude of change between week 5 and week 14 for each the cognitive functioning domains and coping skill acquisition factors. Treatment condition and treatment by time interaction terms will be entered as predictors. This approach is potentially more sensitive to treatment effects since it incorporates each measurement period and effects of time. A treatment effect would be reflected in a significant main effect of either treatment or treatment by time interaction. If appropriate, baseline level of cocaine use will also be included as a covariate to test if it moderates the effect of treatment on the cognitive and behavioral outcome measures.

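### C14 accepts either a treatment main effect or a treatment-by-time interaction as a treatment effect, giving about 9-10% false positives per exploratory measure, and the main effect does not test the stated change from week 5 to week 14

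*SAP*

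**What the plan says.** C14 states its target plainly. For each cognitive domain and coping factor separately, the analyses will "test the effect of treatment condition on the magnitude of change between week 5 and week 14". Treatment and treatment by time both enter a mixed model, and the decision rule is: "A treatment effect would be reflected in a significant main effect of either treatment or treatment by time interaction". C14 justifies the approach this way: "This approach is potentially more sensitive to treatment effects since it incorporates each measurement period and effects of time". It gives no significance level, no order of testing and no correction for the pair of tests.

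C13 schedules these measures at baseline, week 5 and week 14, and identifies week 5 as the beginning of the medication phase. The Protocol agrees (Design Overview, Randomization): patients in the MAS-ER arm "will begin receiving medication at the start of week 5". C13 does say that "multiple comparison corrections will be used to reduce the chance of Type I errors", but for its own analyses, in which baseline and week 5 values predict treatment response.

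**The concern.** The decision rule does not match the target. A difference between arms in change is the treatment-by-time term. The main effect answers another question, and with these visits a large part of the answer comes from a time when medication has only just begun.

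The rule also gives each measure two chances to succeed, so the false-positive rate is higher than for one test. At stake is what the trial will say about whether MAS-ER alters cognition and coping skills. For the coping scale, C13 writes: "This scale will be of primary importance to assess the extent to which the treatments differentially impact the development of coping skills".

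**Working it through.** **Benchmark.** C14 gives no error rate to reproduce. C8 states a significance level of 0.05. Recomputing C8's comparison (37% versus 10%) at two-sided 5% with 50 per arm gives 90.2% power, matching the stated 90%. With 34 per arm it gives 75.9% (pooled variance) or 78.2% (arcsine) against the stated 80%. One-sided testing would give 94.8% at 50 per arm. Two-sided 5% is therefore taken as the convention.

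**Inputs.** 50 per arm (C7: 100 randomized, equal split assumed) and 34 per arm (C8). Assumed, because the documents give nothing for these measures: within-patient correlation ρ between weeks 5 and 14 of 0.3 to 0.8; a week 14 effect of d = 0.57, borrowed from C8, where it belongs to the week 4 response analysis; and 32% missing at week 14, from (100 − 68)/100, with 68 being the completers required in the Protocol's Description of Subject Population.

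**Step 1: content of the main effect.** Let D5 and D14 be the arm differences at the two visits. The change contrast is D14 − D5.
- Time coded 0 at week 5: main effect = D5.
- Averaged over the two visits: main effect = (D5 + D14)/2.

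Neither is a change. As an illustration, put a constant offset of 0.3 SD between arms at both visits, with no effect on change. The either/or rule then declares an effect in 30-43% of simulated trials (34 or 50 per arm, ρ 0.5-0.7), while the interaction test stays near 5%.

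**Step 2: error per measure, each test at 5%.**
- Averaged coding, equal variances: Cov[(D5 + D14)/2, D14 − D5] = (Var D14 − Var D5)/2 = 0. The tests are independent, so the error is 1 − 0.95² = 9.75%. The main effect alone accounts for 0.05 × 0.95 = 4.75 of those points, about half.
- Week 5 coding: the correlation between the tests is −√((1 − ρ)/2), which is −0.5 at ρ = 0.5. The bivariate normal probability that either test is significant is 8.8%, 9.1%, 9.4% and 9.5% at ρ = 0.3, 0.5, 0.7 and 0.8.
- Strongly correlated tests: 8.3% with week 5 coding at ρ = 0, and 8.2-8.7% with averaged coding if the SD doubles by week 14.
- Simulation at 34 and 50 per arm: 9.5-10.3% (averaged, two or three visits) and 8.7-9.6% (week 5 coding). With 32% missing at week 14: 8.5-9.9%.

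**Step 3: several independent measures (averaged coding).**

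| Measures tested | One test each | Either/or rule |
|---|---|---|
| Seven instruments | 1 − 0.95⁷ = 30% | 1 − 0.95¹⁴ = 51% |
| Three domains | 1 − 0.95³ = 14% | 1 − 0.95⁶ = 26% |

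The seven are Letter-Number Sequencing, delay discounting, Wisconsin Card Sort, BRIEF-A, Drug Stroop, IRAP and CSS. The three are executive functioning, implicit cognition and coping.

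**Step 4: power at d = 0.57, 50 per arm, complete data (simulated).**

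| ρ | Interaction only | Either/or, averaged | Week 14 adjusted for week 5 |
|---|---|---|---|
| 0.3 | 66.0% | 80.3% | 83.5% |
| 0.5 | 80.1% | 87.2% | 89.9% |
| 0.7 | 95.4% | 96.8% | 97.5% |
| 0.8 | 99.4% | 99.6% | 99.7% |

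The adjusted test has an error of 4.9-5.3%. With 32% missing, power is 66.4-97.1% for the adjusted test and 67.6-97.1% for either/or. The greater sensitivity that C14 expects is therefore available from one test at about half the error.

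**The case against.** The strongest reply is that C13 and C14 are labelled exploratory and C14 promises no error rate, so 5% is a standard it never set. That stands as a limit on importance. The importance C13 gives the coping scale does not make it a confirmatory endpoint. It does not rescue the rule, however. C14 names significance as the criterion, and the equally exploratory C13 applies a correction, so the authors regard Type I error as relevant at this level.

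The week 5 assessment might also fall after the first doses, since the documents do not fix the day. D5 could then hold a small early drug effect. It would still not be change from week 5 to week 14.

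A reader might infer more than the documents support:
- *That the rule causes a 51% chance of a false finding.* With one test on each of seven independent measures the chance is already 30%. The rule adds 21 points, or 12 points with three domains. C14 speaks of domains and factors, so seven is only one reading.
- *That the two faults add up.* Under randomization the week 5 difference is chance and is already counted in the 9-10%. The content of the main effect is a problem of interpretation, not a further error rate.
- *That the weekly C12 outcomes are affected in the same way.* C14 does say "The analysis of secondary outcomes collected over time will be based on Mixed Effect Models (MEM) for longitudinal data". For weekly measures over weeks 5-14, though, nearly all values follow the start of medication, and a treatment effect averaged over those weeks is a legitimate contrast.

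**Conclusion.** The point holds for the cognitive and coping measures in C14. The stated rule contradicts the stated target and gives about 9-10% false positives per measure instead of 5% (about 8-9% if the two tests are strongly correlated). About half of the false positives under averaged coding come only from a term that does not measure change. A chance imbalance at week 5 could be reported as an effect of MAS-ER.

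The size rests on 5% per test, taken from C8, and on assumed correlations and variances; the range of results across those assumptions is narrow. The count of measures drives the overall error and is open to interpretation. The primary logistic model in C10 is untouched: its displayed form has no interaction, and testing its single treatment coefficient is sound. This is a fault worth correcting in an exploratory section, not a threat to the trial's main conclusion.

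**What to change.** Replace the decision sentence in C14 with: *For each cognitive and coping measure the treatment effect is tested once, as the MAS-ER minus placebo difference at week 14 adjusted for the week 5 value (mixed model with week 5 as covariate or with a common week 5 mean). The treatment main effect is not counted as a treatment effect for these measures.*

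The cost is wording only. With complete data, power at d = 0.57 and 50 per arm is 0.1 to 3.2 points higher than under the either/or rule; with 32% missing at week 14 it is within about 1.3 points. A drug effect already present at the week 5 assessment would be partly adjusted away, which is consistent with the plan's use of week 5 as the start of the medication phase.

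A multiplicity correction across measures is a separate, optional decision and has a real price. Bonferroni over seven measures (C13 names no method, so this is an assumption) would lower power from 84-90% to 59-69% at 50 per arm, d = 0.57 and ρ 0.3-0.5. No change to the weekly C12 outcomes is needed on this account.

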This proposal will be one of the first investigations to employ a sequential and integrative treatment strategy in which a medication targeting dopamine release will be used to enhance the efficacy of a behavioral intervention among individuals not responding to the behavioral treatment alone. We propose a Stage 2 treatment development trial in which 155 treatment-seeking cocaine dependent participants will enter behavioral therapy based on the Community Reinforcement Approach (CRA + CM). Those who fail to achieve sustained abstinence after the first 4 weeks will continue with the behavioral treatment (CRA + CM) and be randomly assigned to receive either mixed amphetamine salts-extended release (MAS-ER) or placebo, over a 10-week double-blind trial.

The Primary Aim is to test the following hypothesis

Among cocaine dependent patients who have failed to respond to an initial trial of behavioral therapy (CRA + CM), a greater proportion in the enhanced behavioral treatment condition (CRA+CM/MAS-ER) will achieve 3-weeks or more of continued abstinence compared to patients treated with CRA+CM/PLACEBO.

We will also investigate cognitive and behavioral predictors of response to the behavioral therapy alone and the effect of medication enhancement on other indicators of treatment response: urine confirmed weekly cocaine use, craving, quality of life, and treatment retention. Potential moderators and mediators of an enhanced behavioral treatment effect, including cognitive functioning, the use of relapse prevention skills, and changes in patient commitment language will be tested.

Description of Subject Population

Sample #1

Specify subject population

Cocaine Dependent Treatment Seekers

Number of completers required to accomplish study aims

68

Projected number of subjects who will be enrolled to obtain required number of completers 155

Age range of subject population

18-60

Gender and Ethnic Breakdown

Males (total n=116): Hispanic n=35; Non-Hispanic n =81

Females (total n=39): Hispanic n=12; Non-Hispanic n= 27

American Indian: n=0

Asian: n=6 (Males=5; Females=1)

Native Hawaiian: n=0

African American: n=79 (Males=59; Females=20)

White: n=70 (Males=52; Females=18)

Description of subject population

We plan to enroll 155 adult participants who are actively using cocaine (evidenced by positive urine toxicology), are currently seeking treatment for their drug use and who meet eligibility criteria

Recruitment Procedures

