outcome (at least 3 consecutive weeks of urine toxicology confirmed self-reported abstinence) will be examined using logistic regression adjusted for covariates (e.g., baseline days/week of cocaine use):  $logit(Y_{ikt}) = \beta_0 + \beta_1 I_{ij}^M + \beta_2 Z_{ijk} + e_{ijk}$ ; where  $Y_{it}$  is a binary outcome indicating 3 weeks of abstinence ( $Y_{itk} = 1$ , when a given individual in a treatment condition is abstinent),  $I_{ij}^M$  is an indicator for the medication treatment ( $I_{ij}^M = 1$  for MAS-ER and  $I_{ij}^M = 0$  for PLACEBO), ),  $Z_{ijk}$  is a vector of covariates, such as baseline cocaine use, and demographic characterisitics (age, gender, ethnicity), and  $e_{ijk}$  is random error. [Covariate by treatment interactions will be tested for significance and the main effect, the primary hypothesis will be answered by testing the null hypothesis  $B_1=0$ . ]

- **[C11. Predicting Responder and Non-Responder status.** Analyses will be conducted to identify variables that may help predict who is more or less likely to respond to the psychosocial intervention alone. Identifying key cognitive-verbal mechanisms (see below) that predict treatment response can help provide important avenues for guiding future therapy development. This important aim will be examined using a logistic regression model within a general linear model framework where responder status at the end of week 4 is a binary outome and the predictors will be a vector of baseline covariates. Predictor variables will be entered in blocks and tested for significance (baseline commitment language, executive functioning, implicit cognition, coping skills, baseline cocaine use, and demographic characteristics (age, gender, ethnicity). Furthermore, a vector of variables representing the magnitude of change in the cognitive, behavioral, and verbal mechanisms will be tested. This later block of variables will evaluate if the response to the behavioral intervention alone is predicted by the magnitude of change in the key cognitive, verbal, and behavioral indices.]

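### SAP C13 and C14 do not state the treatment-by-moderator term their moderation questions need, so, run as written, they cannot tell a moderator from a prognostic variable

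*SAP*

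**What the plan says.** The protocol, under Specific Aims and Hypotheses, commits to testing this: "Potential moderators and mediators of an enhanced behavioral treatment effect, including cognitive functioning", together with relapse prevention skills and changes in commitment language.

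Three SAP sections bear on how that is done.

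- **C13** sets out to "evaluate the predictive and/or moderating relationship of several key cognitive, verbal, and behavioral mechanisms on treatment response". The analysis it then describes is: "For this set of analyses Baseline and Week 5 assessments will be used to predict treatment response". It promises that "multiple comparison corrections will be used to reduce the chance of Type I errors", without naming a method. It gives no model equation and mentions neither a treatment term nor a product term.
- **C14** covers the cognitive and coping outcomes from week 5 to week 14. Its model terms are stated: "Treatment condition and treatment by time interaction terms will be entered as predictors". Then, if judged appropriate, "baseline level of cocaine use will also be included as a covariate to test if it moderates the effect of treatment" on those outcomes.
- **C10**, for the primary abstinence outcome, does name interactions: "Covariate by treatment interactions will be tested for significance". The covariates it gives as examples are baseline cocaine use, age, gender and ethnicity.

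**The concern.** Moderation means that the treatment effect differs by the value of some variable. A covariate entered as a main effect shifts the outcome equally in both arms and leaves one common treatment effect. It therefore does not carry out the test that C14 says it is for. Predicting response from a baseline score, as in C13, has the same limit.

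An analyst who followed the text literally would have one significance test that responds to prognosis and to moderation alike. The moderator aim matters to this trial's rationale: the protocol background says the earlier medication benefit was most marked in the more severely dependent patients, and the SAP wants its predictors to guide later treatment development. A prognostic variable taken for a moderator would point that work at the wrong patients.

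**Working it through.** **Inputs.** From the SAP: 100 randomized patients (C7), 50 per arm, response 37% against 10%, alpha 0.05 (C8). C8 does not state sidedness; two-sided is assumed. The plan gives no power or sample size for any moderator analysis, so there is no plan figure to reproduce. All moderator effect sizes below are assumptions.

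**Step 1: what each model can express.** Let T be treatment (0 or 1) and Z the standardized candidate moderator.

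- Covariate model: E(Y) = b0 + b1·T + b2·Z. The treatment effect is b1 at every Z.
- Product model: E(Y) = b0 + b1·T + b2·Z + b3·T·Z. The treatment effect is b1 + b3·Z, and moderation is b3 ≠ 0.

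C14 concerns change over time, so the treatment effect on change is the treatment-by-time coefficient. For Z to modify that, a Z × treatment × time term is needed.

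**Step 2: why the main effect is ambiguous.** With equal arms and slopes s0 (placebo) and s1 (MAS-ER), the covariate test targets roughly (s0 + s1)/2 and the product term targets s1 - s0.

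- Prognostic only, slopes 0.3 and 0.3: average 0.3, difference 0.
- Moderator in one arm, slopes 0 and 0.6: average 0.3, difference 0.6.
- Crossover moderator, slopes -0.3 and +0.3: average 0, difference 0.6.

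The first two give the covariate test the same target. The third gives it nothing to find.

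**Step 3: hand check, continuous outcome, residual SD 1.** The standard error of the common slope is about 1/√100 = 0.10. That of the slope difference is about √(1/50 + 1/50) = 0.20.

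- Prognostic slope 0.4: z = 0.4/0.10 = 4.0, so power is about Φ(4.0 - 1.96) = 98% on the covariate test and 5% on the product term.
- Crossover ±0.3: z = 0 on the covariate test, so about 5%. On the product term z = 0.6/0.20 = 3.0, so power is about Φ(3.0 - 1.96) = 85%.

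**Step 4: simulation, 50 per arm, two-sided 5%.** Logistic rows use 37% against 10% response.

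| Scenario | Covariate test | Product term |
|---|---|---|
| Continuous, prognostic only, slope 0.4 | 97% | 5% |
| Logistic, prognostic only, odds ratio 2 per SD | 77% | 6% |
| Logistic, prognostic only, log-odds slope 0.8, no treatment term in the covariate test | 82% | 4% |
| Continuous, crossover, slopes +0.3 and -0.3 | 5 to 6% | 82 to 83% |
| Continuous, slope 0.6 in one arm only | 79% | 83% |
| Logistic, log-odds slope 1 on MAS-ER only | 72% | 38% |

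The simulated continuous figures agree with the hand check to within about 3 points.

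**Step 5: does C10 fill the gap?** Its interactions apply to the abstinence model. They do not reach the C14 cognitive and coping outcomes, and its named covariates do not include the C13 cognitive, verbal or coping measures.

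**The case against.** The strongest reply is that the wording is incomplete rather than wrong. C14's declared purpose is a moderation test, entering a variable as a covariate does not forbid also entering its product with treatment, and C10 shows the authors know the term. C13 gives no equation at all. This stands in part: an interaction may have been intended. But C14 lists its terms and the needed one is not among them, so the plan still has to say it.

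Three stronger readings are tempting, and the documents do not support them.

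- *The SAP has no treatment-by-covariate interaction.* It has, in C10. C10's covariate list is illustrative, and C7 lets significant baseline predictors of the primary outcome be considered as covariates, so some other measures could enter. That route screens on main effects, however, which would tend to drop a pure moderator, and it serves the abstinence outcome only.
- *The planned tests cannot detect a moderator.* A moderator acting in one arm also produces a main effect, and the covariate test can then be significant more often than the product term (72% against 38% in the table). What it cannot do is say which of the two it has found.
- *Prognostic variables will be reported as moderators.* No passage says that a main effect will be labelled that way. That is a risk of literal execution, not a stated rule.

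The stakes are also limited: both sections are labelled exploratory, C14's sentence is conditional, and C13 promises a multiplicity correction.

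**Conclusion.** The point holds in a bounded form. C13 and C14 omit the treatment-by-moderator term, and without it a significant result cannot be read as moderation. At 50 per arm a purely prognostic variable would be significant in about 77% to 97% of trials on the covariate test, against about 5% on the product term. A pure crossover moderator of a continuous outcome would be found in about 5% against 83%.

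These figures rest on assumed slopes, a standardized covariate, complete data on 100 patients and single tests at two-sided 5%. The size of the contrast changes with the assumptions; the inability to separate prognosis from moderation does not, because it follows from the model terms. The test of the primary hypothesis (B1 = 0) does not depend on C13 or C14 and is unaffected.

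**What to change.** - **C14:** include baseline use, baseline use × treatment and baseline use × treatment × time (with the lower-order baseline use × time term that the three-way product requires). Judge moderation only on the terms that contain both baseline use and treatment.
- **C13:** for each mechanism, fit response on treatment, mechanism and treatment × mechanism. Call it a moderator only on the product term. Apply the promised multiplicity correction to those terms and name the method.
- **Timing:** when a mechanism is tested as a moderator, use scores taken before the first dose. C13 places the second assessment at week 5, the start of the medication phase, without saying whether it precedes dosing; a score taken after dosing may already reflect treatment.

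The cost is a few sentences and one product term per C13 model, with a small set of terms in C14. The real drawback is power, and the SAP should state it: at N = 100 and 37% against 10%, a log-odds slope of 1 in one arm only gives the product term about 38% power before multiplicity correction. A non-significant product term should therefore not be read as evidence that moderation is absent.
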